10.5. Confidentiality

The study investigator will gather certain personal information about participants. This information will be held by Qualitas/iwi as aggregated data. Data will be identifiable via study number allocated at enrolment but not by participant name. All publicly shared data or data used in publications will be in a non-identifiable form.

Consent is sought for extended use of the data, which means it may be used in future research—for example, an extension of the current study and/or related studies conducted by Qualitas/iwi. Furthermore, data may be used for subsequent statistical analysis, which may be published in peer-reviewed journals; however, no identifiable personal details will be published or used.

Participant data will be stored in the company share drive with access restricted to the researchers involved in the study at the head office of Qualitas Health for a period of 15 years and will be accessed by Trial Co-Investigator and trial contact. At the end of this storage period participant data will be disposed of in a confidential manner.

Unless required by law, only the participants and their authorised representatives, will have access to data which identifies participants by name or from which participant identity is otherwise apparent or can be reasonably ascertained.

All personal information will be used only for the purpose of administering participation in this study and in accordance with the laws governing the protection and privacy of personal information under USA privacy legislation.

By signing the attached consent form, participants authorize the release of/or access to this confidential information in an aggregated non-identifiable form to the relevant study personnel and regulatory authorities as noted above.

Participants have the right to access personal information collected from them in connection with the study and request corrections of any such personal information that is incorrect.

10.6. Termination of the Study

This research project may be stopped for a variety of reasons.

During the trial, any participant that records out-of-range analytical levels will be referred to their GP for assessment of suitability/safety for continuation in the trial.

At the discretion of the GP the participant will either be placed on standard care of cholesterol-lowering medication (and removed from the trial) or continue in the trial on the supplementation.

The participant also has the option to stop supplementation at any point.

11. Investigator Benefits

The investigators are being remunerated to conduct this study. They will not allow a conflict of interest to compromise their position or this research study.

12. Consent

The Principal Investigator, [name], is required to provide participants with all information regarding the nature and purpose of the research study, risks/benefits, and the possibility of alternative treatment; participants should be given the opportunity to discuss these. It must be stated that participants are free to withdraw anytime and that if participants do not participate, they will not suffer any prejudice.

13. Advice and Information - Contact Details

If participants have any further questions regarding this study, please do not hesitate to contact:

[name] –Trial Contact Ph: [contact]

24hr [contact]

If unwarranted side effects occur, please don't hesitate to contact a doctor and the study representative. In the case of an emergency please dial 911.

### Confidential

### 4-Mar-2022

| Table 1-1
Table 2-1
Table 2-2  | Study design  Treatment Plan  Laboratory parameters to be investigated by Imaware   | 7 |
|--|---|---|
| List of figure 1-1   | res
Study design   | 5 |
| List of abb  | reviations  |   |
| AE CSP CSR FAS GCP GLU HbA1c HDL Hs-CRP ITT LDL N N/A Non-HDL-C PP SAE TC TC: HDL TG | Adverse Event Clinical Study Protocol Clinical study report Full Analysis Set Good Clinical Practice Glucose Glycated hemoglobin High-Density Lipoprotein High sensitivity C-reactive Protein Intention-To-Treat Population Low-density Lipoprotein Sample size Not applicable Non-High-density lipoprotein cholesterol Per protocol population Serious Adverse Event Total cholesterol Total cholesterol, high-density lipoprotein ratio Triglycerides |   |
| U.S. FDA
US
VLDL   | the U.S. Food and Drug Administration United States Very-low density lipoprotein  |   |

### 1. Introduction

This statistical analysis plan (SAP) describes all planned analyses for the Clinical Study Report (CSR) of study **ALM-CVH-22**, a multi-center, single arm, open-label post-market evaluation of orally dosed Almega PL on cholesterol and cardiometabolic parameters.

The content of this SAP is based on protocol **ALM-CVH-22** Amendment version 2. All decisions regarding final analysis, as defined in the SAP document, have been made prior to database lock of the study data.

### 1.1. Study design

EPA is a type of omega-3 essential fatty acid known to play a beneficial role in protection against cardiovascular disease. Almega®PL is the only natural source containing EPA as sole n-3 HUFA that is available over the counter for human consumption. We **hypothesized** that AlmegaPL supplementation improves blood markers associated with heart health and inflammation. This post-market open label single armed trial involving 200-300 male and female participants, that will be monitored during the first 6 months following their subscription to Almega®PL.

As part of the **screening procedure**, participants will complete a short questionnaire to make sure they are new iwi users. Any participant who is already using iwi will not be considered in the study. Any participant that has a serious condition (including but not limited to kidney, neurological, immunological, liver, and gastrointestinal disease, any heart condition, or diabetes) will also be disqualified for the program and directed to their doctor. Any participant attempting conception, pregnant or breastfeeding will also be disqualified. All other participants will be accepted into the limited study based on their time of application until the quota is completed. Participation in this study is purely voluntary and participants can withdraw at any point without prejudice.

Participants will be asked to take the allocated product according to the **dose** prescribed (2 capsules per day containing 1000-1100 mg Almega®PL) and adherence to the protocol will be evaluated with a follow up email. Participants will be asked to maintain their usual level of physical activity and diet for the duration of the study. The dose used in this trial is in agreement with the commercial dose communicated to the FDA and comparable to doses previously used in our clinical trials.

Along with the fist supplement order shipped to the new subscriptions, participants will receive the baseline hearth health test kit from ImawareTM. Participants will be contacted 3 and 6 months after and they will be sent subsequent kits once the confirmed adherence to the supplement. The test kits will monitor blood lipid levels across a supplementation period (baseline, month 3 and month 6) thanks to a finger prick blood drawing system. The age, height, weight, gender, fasting total cholesterol, LDL-cholesterol, HDL-cholesterol, calculated VLDL-cholesterol, triglycerides, as well as hs-CRP inflammatory marker, and glucose and HbA1c as diabetes indicator of each participant will be recorded over the study period. **Qualitas Health** will receive the aggregated data of the participants only for statistical analyses at their headquarter in Houston and store it in the company share drive with access restricted to those involved in the study. There will be no cost incurred for this analytical assessment to the participant.

Results for the per intended-to-treat (ITT) population will be first tested for normality before any other test will be conducted and baseline data was compared against month 3 and month 6 data. Based on the distribution of data, either Welch two-sample unequal variance t-tests or Wilcoxon Ranks sum tests will be used to compare two-tailed differences between groups. Differences will be considered statistically significant at a p value < 0.05, but the thresholds for the significance of the 20 clinical outcomes were adjusted for multiple variables by the Bonferroni adjustment method which decrease the significance of p-value from <0.05, down to <0.0025. Intervention

effect will also test using an analysis of covariance model (ANCOVA) adjusting for baseline parameters.

[figure not shown]

Figure 1-1 Study design

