Results for the per protocol (PP) population will be first tested for normality before any other test will be conducted and baseline data was compared again month 3 and month 6 data. Based on the distribution of data, Welch two-sample unequal variance t-tests and Wilcoxon Ranks sum tests were used to compare two-tailed differences between groups. Differences will be considered statistically significant at a p value < 0.05. Intervention effect will also test using an analysis of covariance model (ANCOVA) adjusting for baseline parameters.

10. Study Procedures:

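### An unspecified normality test decides whether the primary triglyceride result is a mean or a rank comparison, and no effect estimate, scale or confidence interval is fixed

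*SAP*

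**What the plan says.** SAP 1.1 Study design: the ITT results "will be first tested for normality before any other test will be conducted". Then: "Based on the distribution of data, either Welch two-sample unequal variance t-tests or Wilcoxon Ranks sum tests will be used". After the significance thresholds it adds that the intervention "effect will also test using an analysis of covariance model (ANCOVA) adjusting for baseline parameters". The thresholds are 0.05 and, after a Bonferroni step for 20 outcomes, 0.0025.

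Protocol section 9 (Study Design) has the same scheme in the per-protocol population, with the two tests joined differently: "Based on the distribution of data, Welch two-sample unequal variance t-tests and Wilcoxon Ranks sum tests were used".

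The objectives tables in both documents define the primary endpoint as triglyceride change from baseline over six months, and hs-CRP change as a secondary endpoint. They do not say whether change means a mean difference, a median shift or a ratio. Neither document mentions a transformation.

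**The concern.** A Welch test and a rank-sum test answer different questions. The first compares means. The second compares distributions through ranks and comes with no effect size unless the plan names one. Under the SAP, a preliminary test on the trial's own data decides which question the primary endpoint answers, and the decision can differ by marker and by visit.

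The preliminary test is itself undefined. Its type and level are missing. So is its target, which could be values at each visit, within-person changes or model residuals. Nothing says what happens if baseline passes and month 6 fails. The ANCOVA does not close the gap, because it is an addition with no rank relative to the two-stage test and no scale.

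This matters more than usual here. The trial is open-label and single-arm, the sponsor's own personnel run the analysis (SAP 2.1), and the SAP introduction says all decisions on the final analysis were made before database lock. This one was left to the data.

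**Working it through.** **1. The plan's own figure.** SAP section 3 uses a two-independent-sample t-test, effect size 0.5, allocation 1:1 and power 95%, and arrives at 210. With 105 per group the noncentrality is 0.5 × √(105/2) = 3.62 on 208 degrees of freedom. At two-sided 0.05 the exact power is 0.9501, so 210 reproduces. Section 3 states no alpha; one-sided 0.05 would need only 176, so two-sided 0.05 is implied.

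**2. Which branch the rule takes.** Inputs not in the documents: log-normal data, log-scale SD 0.3 to 0.6 for triglycerides and 1.0 to 1.2 for hs-CRP, and Shapiro-Wilk at 0.05 on the untransformed values at each time point, with rank-sum chosen if either rejects. With 105 or 210 values per time point, normality is rejected in 99 to 100% of simulated trials. The rank-sum test is then the predictable outcome.

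For mildly skewed markers (log SD 0.10 to 0.20, n = 200) it is not predictable. The pre-test rejected in 32 to 86% of runs, and baseline and follow-up gave opposite verdicts in 22 to 37%.

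**3. What that branch costs.** The planning point of step 1 is placed on the log scale (105 v 105, d = 0.5):

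| Analysis | Power at 0.05 | Power at 0.0025 |
|---|---|---|
| Unpaired t-test on logs | about 0.95 | 0.71–0.73 |
| SAP two-stage rule | about 0.94 | 0.67–0.69 |
| Welch on raw values, triglycerides | 0.91–0.94 | 0.59–0.69 |
| Welch on raw values, hs-CRP | 0.75–0.81 | 0.29–0.38 |

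The rule loses about 1 point at 0.05 and 3 to 4 points at 0.0025. This agrees with theory. The relative efficiency of rank-sum to t on log-normal data is 3/π = 0.955, so 210/0.955 ≈ 220 participants would restore the power. The last two rows show a larger loss, but the pre-test steers skewed data away from that branch.

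**4. If the tests were made paired and the pre-test kept.** Assumed: n = 200; triglycerides log SD 0.5, correlation 0.7, a 7% fall; hs-CRP log SD 1.0, correlation 0.6, a 15% fall. The standardised within-person effect on the log scale is |ln(ratio)| / (SD × √(2(1 − r))):

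- Triglycerides: 0.0726 / (0.5 × √0.6) = 0.187; × √200 = 2.65.
- hs-CRP: 0.1625 / (1.0 × √0.8) = 0.182; × √200 = 2.57.

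Simulated power:

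| Analysis | Triglycerides, 0.05 | Triglycerides, 0.0025 | hs-CRP, 0.05 | hs-CRP, 0.0025 |
|---|---|---|---|---|
| Signed-rank on raw change | 70% | 29% | 61% | 21% |
| Paired t on log change | 75% | 35% | 71% | 31% |

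The loss is 5 to 6 points for triglycerides and 10 for hs-CRP. Separate runs at 0.05 agreed within about 2 points.

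**5. Where most of the power lies.** In the same settings at 0.05, the rank-sum test has 18% for triglycerides and 28% for hs-CRP. The unpaired log t-test has 19% and 29%, and the paired log t-test 75% and 71%. The log scale alone adds about 1 point; using the pairing adds 56 points (75 − 19) and 42 points (71 − 29).

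**The case against.** The best defence is that the rule is data-dependent only in form. Triglycerides and hs-CRP are likely to be skewed, so the rank-sum test would be chosen almost every time. It is robust, gives the same answer on raw and log values, and loses very little to a log-scale t-test. It can also be reported with a Hodges-Lehmann shift and interval. All of that stands. What remains is that the SAP names no such estimate, gives no rule for conflicting verdicts, and leaves the less skewed markers open to either branch.

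A reader might infer that skewness handled this way costs the trial a great deal of power. A paired t-test on raw changes against one on log changes gives, for example, 68% v 75% for triglycerides and 41% v 72% for hs-CRP under the step 4 assumptions. The documents do not support that reading. They name neither paired test, and their own rule would avoid a t-test on clearly skewed raw data.

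A reader might also take it that the pre-test and the ANCOVA run on untransformed values. That is an inference from the absence of any transformation; the SAP speaks only of results and gives the ANCOVA no scale.

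**Conclusion.** The point holds as a gap in pre-specification. The test, the scale and the effect estimate for the primary endpoint are not fixed, and the unranked ANCOVA does not fix them. It should be corrected before analysis.

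The power consequence of the test-selection rule alone is small. It becomes moderate if the tests are corrected to paired forms and the pre-test stays, and the loss in points is similar at 0.05 and at 0.0025. Most of the available gain comes from using the pairing, which is a separate weakness of the two-sample tests. Every power figure rests on assumed log-normal data, SDs, correlations and effects; the conclusion on pre-specification needs none of them.

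**What to change.** In SAP 1.1 Study design, and to match in protocol section 9:

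- Delete the normality pre-test and the choice that depends on it.
- Name one primary within-person analysis: change from baseline in natural log for triglycerides, and the same for hs-CRP, back-transformed to percent change with a 95% CI. Treat VLDL the same way if it is calculated from triglycerides; the documents call it calculated but give no formula.
- Analyse the other markers as paired change on the original scale, with 95% CI.
- Keep the Wilcoxon signed-rank test as a sensitivity analysis, and state the role and scale of any ANCOVA that is retained.

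The cost is wording only, with no new data. The small downside is that effects for the log-scale markers appear as percent change and not in original units, so the report will carry two kinds of effect measure, fixed in advance by marker.

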### 1.1. Study objectives and endpoints

4-Mar-2022

The aim of this study is to assess the effectiveness of Almega®PL on improving blood markers associated with heart health of iwi customers. Specifically, we would like to confirm the decrease in cholesterol observed in our previous trial (Rao et al., 2020) while assessing the capacity to also decrease triglycerides (primary outcome). As a secondary objective we would like to understand if EPA, precursor of signalling molecules involved in the inflammatory response, could help decrease the inflammatory marker hs-CRP.

Objectives and related endpoints are described in Table 1-1 below

Table 1.1-1. Objectives and relative endpoint

| OBJECTIVES   | ENDPOINTS   | JUSTIFICATION FOR ENDPOINTS   |
|--|---|---|
| Primary  |   |   |
| Can Almega® PL
supplement decrease
triacylglycerides in a
generally healthy
population?  | Triglyceride change from baseline over 6-month period.  | Triglyceride levels is an
atherogenic lipid and an
important risk factor in
cardiovascular disease   |
| Secondary  |   |   |
| Can Almega® PL supplement replicate the decrease in VLDL and total cholesterol we observed in our previous clinical trial (Rao et al., 2020)? Will the results from a controlled population translate to the iwi costumers? Can Almega® PL | Total Cholesterol change from baseline over 6-month period. VLDL-Cholesterol change from baseline over 6-month period. LDL-Cholesterol change from baseline over 6-month period. HDL-Cholesterol change from baseline over 6-month period. hs-CRP change from baseline over 6-month period. Fasting glucose change from baseline over 6-month period. HbA1c change from baseline over 6-month period. | Cholesterol in plasma levels is atherogenic and a risk factor in cardiovascular disease. Hs-CRP is an age-related inflammatory market. Omega-3 help regulate the inflammatory response. |

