### 3. Sample size calculation

Power and sample size calculation was performed on the primary outcome (triglycerides) using G\*Power 3.1 (Department of Psychology, University of Düsseldorf, Germany). Sample size calculation was based on a student t-test (two independent samples). Using an effect size of 0.5, and an allocation ratio N2/N1 of 1, the sample size was estimated to be 210 to achieve a power of 95%.

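### The single-arm trial compares the same people's baseline and follow-up with tests for two independent groups, and is sized that way; with positive within-person correlation this wastes power for falls smaller than planned

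*SAP*

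**What the plan says.** SAP section 1 describes the study as "a multi-center, single arm, open-label post-market evaluation of orally dosed Almega PL", and section 1.1 repeats this: "This post-market open label single armed trial involving 200-300 male and female participants". There is no comparator. Each participant is tested at baseline, month 3 and month 6, and the primary endpoint in SAP Table 1.1-1 is "Triglyceride change from baseline over 6-month period".

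For the comparison of baseline with months 3 and 6, SAP section 1.1 states that "either Welch two-sample unequal variance t-tests or Wilcoxon Ranks sum tests will be used to compare two-tailed differences between groups". The statistical paragraph of protocol section 9 has "Welch two-sample unequal variance t-tests and Wilcoxon Ranks sum tests were used to compare two-tailed differences between groups". Both documents add an ANCOVA; in the SAP's words, the intervention "effect will also test using an analysis of covariance model (ANCOVA) adjusting for baseline parameters".

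SAP section 3 bases the sample size on a t-test for two independent samples: "Using an effect size of 0.5, and an allocation ratio N2/N1 of 1, the sample size was estimated to be 210", for 95% power.

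The significance level is 0.05 in the protocol. The SAP lowers it to 0.0025 by a Bonferroni adjustment for 20 outcomes. The protocol analyses the per-protocol population. The SAP analyses an ITT set made up of people with a baseline test and at least one follow-up test (section 2.7.2).

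**The concern.** Welch's t-test and the rank-sum test assume that the two sets of values come from different, independent people. Here both sets come from the same people. The variance of a mean within-person change contains a covariance term that these tests ignore. If a person's baseline and follow-up triglycerides are positively correlated, the unpaired standard error is too large, and so is the p-value. The design collects paired data and the named tests discard the pairing.

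This is more than loose wording, because section 3 makes the same assumption independently, with an allocation ratio between two groups that do not exist. The ANCOVA does not fill the gap. A regression of change on centred baseline could test mean change, but the plan states no model, contrast or hypothesis.

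At stake is a real but modest fall in triglycerides being reported as non-significant, and a stated power that describes a different trial.

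There is a second, unquantified issue. In the SAP's ITT set a participant may lack one follow-up test, so an unpaired comparison can set the baseline of one set of people against the month 6 values of a subset. The documents name routes of loss. Later kits depend on adherence ("they will be sent subsequent kits once the confirmed adherence to the supplement"), and out-of-range results can lead to removal (SAP section 2.10, protocol section 10.6). They give no rates.

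**Working it through.** **Inputs from the documents.** One arm; effect size d = 0.5; allocation ratio 1; N = 210; power 95% (SAP section 3). Two-sided alpha 0.05, or 0.0025 after Bonferroni (SAP section 1.1). Section 3 states no alpha.

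**Assumptions.** The documents give no within-person correlation r, so I use 0.5, 0.6 and 0.7, with 0 and 0.3 as checks. I also assume 210 people with complete data and the same SD, s, at both visits. Effects of 0.2, 0.25 and 0.3 SD are my choice, to show what happens below the planned 0.5.

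**Step 1: reproduce 210.** A two-sample t-test (noncentral t) with d = 0.5, two-sided 0.05 and 105 per group has power 0.950. Total 105 + 105 = 210, an exact match. The figure is correct for two separate groups at alpha 0.05. Under the same two-group model at 0.0025, 105 per group gives power 0.71, and 354 people would be needed.

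**Step 2: standard error.** The unpaired tests use variance 2s²/n. The true variance of the mean change is 2s²(1−r)/n. The ratio of standard errors is 1/√(1−r):
- r = 0: 1.00; r = 0.3: 1.20
- r = 0.5 / 0.6 / 0.7: 1.41 / 1.58 / 1.83

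**Step 3: true type I error at nominal 0.05.** 2Φ(−1.960/√(1−r)) = 0.0056 / 0.0019 / 0.0003 for r = 0.5 / 0.6 / 0.7, and 0.019 at r = 0.3. The error is conservative.

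**Step 4: power with 210 people.** Let δ = d/√(2(1−r)/210). Ignoring the negligible opposite tail, paired power is Φ(δ − z) and unpaired power is Φ(δ − z/√(1−r)), with z = 1.960 or 3.023.

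| True fall | Alpha | Unpaired, r = 0.5 / 0.6 / 0.7 | Paired, r = 0.5 / 0.6 / 0.7 |
|---|---|---|---|
| 0.3 SD | 0.0025 | 0.53 / 0.53 / 0.54 | 0.91 / 0.97 / 0.995 |
| 0.3 SD | 0.05 | 0.94 / 0.96 / 0.98 | 0.99 / 1.00 / 1.00 |
| 0.2 SD | 0.0025 | 0.08 / 0.06 / 0.04 | 0.45 / 0.59 / 0.76 |
| 0.2 SD | 0.05 | 0.55 / 0.56 / 0.57 | 0.83 / 0.90 / 0.96 |

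At the planned 0.5 SD, unpaired power is at least 0.999 at 0.05 and at least 0.98 at 0.0025 for any r from 0 to 0.7. With 200 people, the lower end of planned enrolment, it is at least 0.976 at 0.0025.

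**Step 5: detectable fall.** For 95% power at 0.0025, the unpaired test needs √(2/210) × (3.023 + 1.645√(1−r)) = 0.41 / 0.40 / 0.38 SD. The paired test needs √(2(1−r)/210) × (3.023 + 1.645) = 0.32 / 0.29 / 0.25 SD.

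**Step 6: one worked result.** Suppose the observed mean fall is 0.25 SD. Unpaired: z = 0.25/√(2/210) = 2.56, p = 0.010, not significant at 0.0025. Paired: z = 2.56/√(1−r) = 3.62 / 4.05 / 4.68, p = 0.0003 / 0.00005 / 0.000003.

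**Step 7: skewed data.** I took lognormal values with an assumed SD of the log of 0.5, and ran 3,000 simulated trials per setting. For a 0.2 SD fall on the log scale at 0.0025, rank-sum power is 0.07 / 0.06 / 0.03, against 0.42 / 0.55 / 0.73 for the signed-rank test on log differences. At 0.5 SD, rank-sum power is at least 0.998.

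**Step 8: paired sample size for the planned effect.** With standardised change d/√(2(1−r)) and noncentral t, 95% power for d = 0.5 needs 54 / 44 / 34 pairs at 0.05, or 92 / 75 / 57 at 0.0025. At r = 0 it needs 106 or 179. All are below 200.

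**The case against.** The strongest reply is that nothing material is lost on the plan's own figures. The only effect size in the documents is 0.5, and there the unpaired tests keep at least 0.98 power even at 0.0025. The loss appears only at smaller effects chosen for illustration, and it needs a positive correlation that the documents do not state. At r = 0 the methods nearly coincide. All of this is true and limits the severity. It does not make the tests right: the documents give no reason to treat 0.5 SD as the smallest fall worth detecting, and the study population is described as generally healthy, so smaller falls are plausible.

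A second reply is that the damage depends on the 0.0025 threshold, which is in the SAP only. The threshold makes it worse, but a 0.2 SD fall at plain 0.05 still has power 0.55 unpaired against 0.83 paired at r = 0.5.

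Third, neither document names a primary test, and the ANCOVA would use baseline values. That is fair as far as it goes, but an unspecified model cannot stand in for a stated test. One plausible reading, change regressed on sample-centred baseline with default standard errors, has type I error 0.091 / 0.083 / 0.071 at nominal 0.05 for r = 0.5 / 0.6 / 0.7 (20,000 simulations). The model therefore needs to be written down.

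Fourth, the missing-visit issue concerns the SAP's ITT set. In the SAP's per-protocol set, with all three tests complete, the same people are compared. Nor does pairing alone remove bias from selective loss. In an illustration with no true change, r = 0.6 and the odds of a missing month 6 doubling per SD of baseline, losses of 10% / 20% gave the Welch comparison a bias of −0.04 / −0.08 SD (towards a false fall). The completers' paired t-test had +0.02 / +0.05 SD (towards a false rise) and rejected at 0.0025 in 0.5% / 1.3% of trials, against 0.01% / 0.08% for Welch. This stands, and it is why the fix includes a mixed model for incomplete visits.

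**Conclusion.** The concern holds. The named tests and the sample-size model are for two independent groups, and this trial has one group measured repeatedly. The arithmetic behind 210 is correct, but for another design and for alpha 0.05 rather than 0.0025.

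The power loss depends on positive within-person correlation, which the documents do not quantify. With complete data it acts in the conservative direction only: a real fall below 0.5 SD may be missed. The planned effect remains well powered and enrolment need not change. Any bias from missing visits is unknown in size and direction. This should be fixed before database lock, but it does not threaten the trial's feasibility.

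**What to change.** 1. In SAP section 1.1 and protocol section 9, replace the Welch and rank-sum tests with a within-person analysis of change: a paired t-test, or a Wilcoxon signed-rank test if the differences are clearly non-normal. Analysing log triglycerides is an alternative. Report the mean change (a ratio if logged) with its 95% confidence interval.
2. Name the primary analysis and the primary visit contrast; the text compares both months, while the endpoint speaks of the 6-month period. For an ITT set with missing visits, a repeated-measures mixed model using all available visits is sound, with its missing-at-random assumption stated.
3. Check normality on the within-person differences or model residuals, not on the raw values at each visit.
4. Restate SAP section 3 as a paired calculation giving the assumed SD of change (or r) and the alpha actually used. Planned enrolment can stay.
5. State the ANCOVA model and its hypothesis, or remove it.
6. Tabulate baseline triglycerides by whether the month 6 test is present, with reasons for loss.
7. Confirm before database lock that the laboratory will deliver rows linked by study number and visit. SAP sections 1.1 and 2.12 speak of aggregated data. Protocol section 10.5 says that data are identifiable by study number, which suggests linkage is possible but does not guarantee it.

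The cost is small: edits to three sections, one added table and a data-format request, with no new visits, tests or participants. It depends on the linked rows being available.

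### The SAP's single-step Bonferroni cut-off is valid, but Holm's step-down procedure would keep the same familywise error, lose no rejection and sometimes add some

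*SAP*

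**What the plan says.** Section 1.1 (Study design) of the SAP first sets two-sided significance at 0.05. It then turns to a set of 20 outcomes, whose cut-off it describes as "adjusted for multiple variables by the Bonferroni adjustment method which decrease the significance of p-value from <0.05, down to <0.0025". Every outcome therefore faces the same fixed cut-off, and no step-down or other sequential procedure is named anywhere in the SAP.

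The same section says that "baseline data was compared against month 3 and month 6 data", so there are two comparisons per outcome. The objectives table lists one primary endpoint ("Triglyceride change from baseline over 6-month period") and seven secondary endpoints: total, VLDL, LDL and HDL cholesterol, hs-CRP, fasting glucose and HbA1c. The SAP does not list the 20 outcomes, and it specifies no simultaneous confidence intervals.

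**The concern.** The sponsor hypothesises that the product improves blood markers of heart health and inflammation in general, and tests a panel of them at two time points. If the hypothesis is right, several of the tested outcomes truly change. Single-step Bonferroni holds each of them to 0.05 divided by the full number of outcomes, however many have already been declared significant. Holm relaxes the cut-off after each rejection without spending more error.

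At stake is some power for the outcomes further down the ordered list. The outcome with the smallest p-value is not affected, and neither is the validity of any claim the SAP would make.

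**Working it through.** **1. The plan's own figure.** 0.05 / 20 = 0.0025, which reproduces exactly.

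**2. What Holm does.** Order the m p-values from smallest to largest. Compare the j-th with 0.05 / (m − j + 1) and stop at the first failure. With m = 20:
- first step: 0.05 / 20 = 0.0025, the same as Bonferroni
- after 10 rejections: 0.05 / 10 = 0.005
- after 19 rejections: 0.05 / 1 = 0.05

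**3. No rejection is lost.** Every Holm threshold is at least 0.05 / m. If Bonferroni rejects k outcomes, their p-values are the k smallest and all are at or below 0.05 / m, so each passes its Holm step.

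**4. The error rate is kept.** Suppose m0 outcomes have no true change. When the first of these is wrongly rejected, at most m − m0 outcomes have been rejected before it, so its p-value is at or below 0.05 / m0. The chance that any of the m0 p-values is that small is at most m0 × 0.05 / m0 = 0.05, whatever the dependence. In 100,000 simulated trials per setting with no true change in any of 20 outcomes, both methods gave 0.049, 0.036 and 0.018 at correlation 0, 0.5 and 0.8.

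**5. Size of the gain.** The documents give no within-person effect size, correlation or number of outcomes that truly change, so these inputs are assumed: paired two-sided tests, N = 200 (the lower end of the planned 200-300), true change 0.25 SD, equal correlation 0 to 0.8.

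Bonferroni power per true effect:
- expected z = 0.25 × √200 = 3.54
- 20 outcomes: critical z at 0.0025 is 3.02; power = Φ(3.54 − 3.02), about 70%
- 8 outcomes: 0.05 / 8 = 0.00625, critical z 2.73; power = Φ(3.54 − 2.73), about 79%

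Holm, by simulation (40,000 trials per setting, no Bonferroni rejection lost), as average power gained per true effect:

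| Outcomes in family | Truly changing | Gain over Bonferroni (points) |
|---|---|---|
| 20 | 1 | about 0 |
| 20 | 5 | 1 to 2 |
| 20 | 10 | 3 to 4 |
| 20 | 16 | 6 to 9 |
| 20 | 20 | 10 to 16 |
| 8 | 2 | about 1 |
| 8 | 8 | 8 to 12 |

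With 10 of 20 changing, 3 to 4 points is an average of 10 × 0.03 = 0.3 to 10 × 0.04 = 0.4 extra true outcomes declared per trial.

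**6. Role of correlation.** With the same inputs, Holm's power at correlation 0, 0.4 and 0.8 is:
- all 20 changing: 85.6%, 82.5%, 79.5%
- 16 of 20 changing: 78.7%, 77.4%, 76.1%
- 8 of 8 changing: 91.3%, 88.8%, 86.3%

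Bonferroni stays at about 70% (20 outcomes) and 79% (8 outcomes), so here the gain shrinks as correlation rises.

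**7. Sensitivity.** The sample-size section of the SAP assumes two independent groups, "Using an effect size of 0.5, and an allocation ratio N2/N1 of 1", with 210 in total. That layout does not match a single-arm before-after study, but it gives a second set of inputs. With 105 per group, d = 0.5 and 20 outcomes, Bonferroni power per true effect is about 72.6%. Holm adds 1.2 to 1.7 points with 5 changing, 3 to 4 with 10, and 9 to 16 with all 20 (correlation 0 to 0.8). At an assumed d = 0.3, Bonferroni has about 20% power and Holm adds 0 to 2 points with up to 10 changing, and 2 to 6 with all 20. In both cases the chance of at least one true finding is essentially the same under the two methods, because Holm's first step also uses 0.0025.

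**The case against.** The strongest reply is that this is a preference. Bonferroni is a recognised, pre-specified control of familywise error, it gives one cut-off that is easy to state, and it has simple simultaneous intervals that agree with the tests. Holm has no equally simple matching intervals. The gain is also negligible unless many outcomes truly change, and the documents support no such assumption: the lipid decreases they report from the earlier trial are in total and VLDL cholesterol only. All of this stands. It limits the point to an improvement of modest and uncertain size. The loss of matching intervals costs little here, because the SAP plans none.

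A reader might infer that correlated lipid outcomes are the reason to prefer Holm. They are not. Holm applies the Bonferroni bound at each step and makes no use of correlation; recovering that conservatism would need a resampling or other correlation-based method.

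A second objection is that changing the method does not repair the sentence. It counts 20 outcomes, while the objectives table lists 8 endpoints, or 8 × 2 = 16 comparisons over two time points. It also does not say whether triglycerides are in the family. If they are, a single Holm family would make the triglyceride decision depend on the other outcomes. That stands too, and those questions should be settled with this one. They do not remove the point, because Holm is at least as powerful as Bonferroni for whatever family is chosen.

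**Conclusion.** The point holds as a cheap improvement to a valid plan. That Holm keeps the familywise error at 0.05 and rejects at least what Bonferroni rejects is a mathematical fact and needs no assumption about the data.

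The size does need assumptions. With 0.25 SD changes, 200 participants and correlation 0 to 0.8, the gain is about 0 to 4 points of power per true effect when up to half of 20 outcomes change. It reaches 6 to 16 points only when most or all do.

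A reader might go further and conclude that the SAP's method is wrong, or that it will cause many real changes to be missed for nothing in return. The documents do not support either reading. The method is valid, it offers a fixed cut-off and simple matching intervals, and nothing in the documents shows that most of the 20 outcomes will change.

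**What to change.** Before database lock and before results are seen, replace the Bonferroni statement in SAP section 1.1 (Study design) with wording such as: *Holm step-down procedure at familywise 0.05 across the pre-specified family of outcomes; Holm-adjusted p-values will be reported. Any 95% confidence intervals are not adjusted for multiplicity.* The interval label is needed because an unadjusted interval can exclude zero when the Holm test is not significant.

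The cost is one sentence. Adjusted p-values need only a sort, a multiplication and a running maximum, which a spreadsheet can do from the SPSS output. The price is that there is no single cut-off to quote, and simple simultaneous intervals will not match the Holm decisions.

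In the same edit, list the outcomes and time points in the family and state the alpha for triglycerides. Both are separate points, but the Holm sentence cannot be applied until the family is listed.
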